- There is no increase in suicidal intensity or new occurrence of suicidal ideation as assessed by C-SSRS
- No clinically relevant QTcF prolongation (QTcF≥500 msec or increase in QTcF from baseline≥60 msec)
- No clinically relevant abnormalities in blood pressure (BP) (90≤Sysotlic BP (SBP) ≥180 mmHg or 50≤Diastolic BP (DBP) ≥105 mmHg or increase or decrease in SBP of at least 20 mmHg or increase or decrease in DBP of at least 15 mmHg from baseline) or any increase in BP that is accompanied by symptoms, such as headache, dizziness, nausea, visual disturbances or other neurological symptoms
- The investigator does not identify any other AEs that require continued monitoring

If the participant cannot be released from the clinical site 4 hours after dosing, extended safety monitoring will be performed as described below.

The post-dose follow-up period will continue for 4 weeks (28 days) after treatment. On-site visits to assess efficacy and safety are scheduled on Day 2 (24 hours post-dose) and subsequently every week (i.e., on Days 8, 15, 22 and 29) during the follow-up period. The assessment to address the primary objective will be performed at Day 2 (24 hours post-dose). Phone calls will be conducted 3 days after each on-site visit with the exception of End-of-study (EOS) visit. The EOS visit will be completed on site on Day 29. The total duration of the study is approximately 8 weeks (56 days), including screening.

Extended safety monitoring in case of AEs on Day 1 (4 hours after dosing)

If extended monitoring is required beyond the minimum 4 hours of monitoring on Day 1, the following will be assessed:

- Monitoring of CNS adverse events (dissociation, amnesia, sedation):
 - If there are any dissociative AEs, amnesia or somnolence/sedation present, the participant should be monitored at the clinical site until these AEs are fully resolved. If the dissociative AEs or cognitive symptoms do not resolve within 6 hours after onset, the participant will be required to stay at the clinical site for overnight monitoring and can be discharged after the assessments are completed on Day 2 and the AEs have resolved. The onset and resolution time of dissociative and cognitive AEs should be captured as accurately as possible. The following assessments are recommended to follow CNS AEs, whenever possible (e.g., participant is awake):

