- If dissociative AEs are present, it is recommended to administer the CADSS every hour until the total score returns to baseline or normal level (i.e., total score not higher than 4)
- If memory gaps/amnesia is present, it should be assessed with orientation questions at least once per hour until the amnesia is resolved
- Sedation/somnolence should be assessed by questioning or the administration of the MOAA/S every hour until the AE is resolved
- Monitoring of suicidal ideation or behavior:
 - If moderate to severe suicidal ideation or any suicidal behavior is present, either based on rating scales or investigator judgment, the investigator must hospitalize the participant at least overnight
 - If suicidal ideation is mild, either based on rating scales or investigator judgment, the investigator's judgment can be used to allow the participant to leave the clinical setting, but in that case arrangements should be made such that family members or friends are present with the participant for at least 24 hours. If such arrangements cannot be made, it is recommended that the participant is hospitalized at least overnight
- Monitoring of QTcF prolongation:
 - If the initial QTcF prolongation is confirmed by repeated ECG at least 10 minutes later, close observation of the participant should be initiated at the investigator's discretion
 - ECG should be performed every 30 minutes until QTcF is below 500 msec and the increase from baseline is less than 60 msec
 - Serum electrolyte levels should be determined and corrected, if needed (in particular hypokalemia, hypomagnesemia)
 - Consultation with a cardiologist can be performed at the investigator's discretion
- Monitoring of increased blood pressure:
 - Increase in blood pressure should be monitored but initial treatment is not recommended unless clinically indicated. Blood pressure increase associated with MIJ821 treatment is usually transient and the blood pressure typically returns to predose values within 3-4 hours
 - At 1.5 hours post-dose, if SBP is ≥160 mmHg and/or the DBP ≥100 mmHg, assessments should continue every 30 minutes until:
 - 1. The blood pressure is <160 mmHg SBP and <100 mmHG DBP, or
 - 2. As per investigator's clinical judgment, the participant is clinically stable, or
 - 3. The participant is referred for appropriate medical care, if clinically indicated

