6.1.4 Treatment duration

Participants will receive a single s.c. injection on Day 1.

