In case of a safety concern or worsening of depressive symptoms including suicidal ideation, participants' hospitalization should be prolonged or they can be re-hospitalized at any timepoint of the study overnight or for a longer period until they improve clinically, as per investigator clinical judgement. If suicidal symptoms are present to a moderate to severe degree, either based on rating scales or investigator judgment, and such symptoms persist throughout the above mentioned monitoring period following the intravenous infusion, investigators must hospitalize participants at least overnight. If suicidal symptoms are mild, either based on rating scales or investigator judgment, the investigator's judgment can be used to allow the participant to leave the clinical setting, but in that case arrangements should be made such that family members or friends are present with the participant for at least 24 hours. If such arrangements cannot be made, it is recommended that the participant is hospitalized at least overnight.

Caution with performance of potentially dangerous tasks

Given that MIJ821 may impair the mental or physical abilities required for the performance of potentially dangerous tasks such as driving a car or operating machinery, participants should be advised about these potential risks. If the participant is feeling drunk or dizzy or if he/she experiences visual disturbances, hallucinations, or euphoric mood, then he/she should not drive, use machines or perform any other tasks that require his/her attention and good coordination.

In case of a safety concern, the participant should be hospitalized (or hospitalization should be prolonged) as per investigator's judgement until resolution of these events or absence of a safety risk.

Scales / tools to assess CNS related AEs

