#### 2.5.1.1 Derivation of MADRS total score

The MADRS consists of 10 items that cover all the core depressive symptoms (apparent sadness, reported sadness, inner tension, sleep, appetite, concentration, lassitude, interest level, pessimistic thoughts, and suicidal thoughts). Each item is scored from 0 (item is not present or is normal) to 6 (severe or continuous presence of the symptom). For each item, a higher score represents a more severe condition.

The MADRS score will be measured at Screening, Baseline (Day 1, -1 hour), 4-hour post-dose on Day 1, 24 hours post-dose and follow-up visits on Day 8, Day 15, Day 22 and Day 29 (EOS).

The 4-hour post-dose assessment will use the '4-hour' questionnaire which is based on participant's condition as observed over the past 4 hours. Two items (reduced sleep and reduced appetite) are not applicable for 4-hour post-dose assessment and will be imputed based on the value of respective 1-hour pre-dose assessment.

[figure not shown]
The 24 hours post-dose assessment is based on the participant's condition as observed since the last evaluation. For all other assessments, a 7-day recall period is used.

A total score (ranges from 0 to 60) is calculated by adding the scores of all 10 items. The following proration formula will be applied to calculate the total score in the case when one of the item scores is missing:

[figure not shown]
$$\text{Total score} = \text{Sum of scores from items present} * (10 / \text{number of items present}).$$

Otherwise if 2 or more items are missing, the total score will be set to missing.

[REDACTED]

[REDACTED]

[REDACTED]

[REDACTED]

[REDACTED]

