### 2.7.4.3 Clinician Administered Dissociative States Scale

The Clinician Administered Dissociative States Scale (CADSS) is a questionnaire that assesses dissociative effects might related to MIJ821. The CADSS comprises 23 subjective items and participant's responses are coded on a 5-point scale (0=" Not at all", 1=" Mild", 2="Moderate", 3="Severe" and 4="Extreme") based on their current experience. The CADSS will be assessed at baseline (Day 1, -1 hour pre-dose), 0.5 hour, 1.5 hour and 4-hour post-dose on Day 1, and follow-up assessments at Day 2 (24-hour), Day 8, Day 15, Day 22 and Day 29.

The CADSS can be divided into 3 components using the following scoring method defined in [Table 2-9](#). A higher score represents a more severe condition. Missing data at any subjective item will be unlikely since the items could not be skipped during the interview unless raters provide rationales, in which case the component scores and the total score will be calculated based on the proration approach. Specifically, if the percentage of missing items is more than 10% of the total number of items for the component score, no imputation will be made and the component score will be missing. Otherwise, the sum of available items will be used and the component score is calculated as follows:

$$\text{Component score} = \text{Sum of scores from items present} * (\text{total number of items in the component} / \text{number of items present}).$$

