### 2.7.4.4 Modified Observer's Assessment of Alertness/Sedation

The Modified Observer's Assessment of Alertness/Sedation (MOAA/S) will be used to assess participant responsiveness and measure sedation associated with MIJ821. The MOAA/S scores

range from 0 [No response to painful stimulus] to 5 [Readily responds to name spoken in normal tone (awake)]. A lower score of MOAA/S indicates more severe condition of sedation.

The MOAA/S will be taken at the same visits and time points as CADSS. The following summary table and/or plots will be provided:

- A stacked bar plot for categorical MOAA/S score by treatment arm and analysis visit.
- Summary table and bar-plot comparing the percentage of participants with any sedation (MOAA/S≤4) across treatment arms over time.
- Summary table and bar-plot comparing the percentage of participants with severe sedation (MOAA/S≤2) across treatment arms over time.

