#### 2.7.4.5 Columbia-Suicide Severity Rating Scale

The Columbia-Suicide Severity Rating Scale (C-SSRS) is a questionnaire that prospectively assesses suicidal ideation and behavior (SIB) and non-suicidal self-injurious, as well as intensity assessments for suicidal ideation, as summarized in [Table 2-10](#) below. The 11 preferred SIB categories include five levels of suicidal ideation, five levels of suicidal behavior and the category non-suicidal self-injurious. Each category has a binary response (yes/no). For this study, participants who have suicidal ideation with intent (answered ‘Yes’ for question 4 or 5) at baseline will be excluded from the study as screening failure.

The C-SSRS will be assessed at Screening, Baseline (Day 1, -1 hour pre-dose), 4-hour post-dose on Day 1, and follow-up visits at 24 hour (Day 2), Day 8, Day 15, Day 22 and Day 29 (EOS). The SIB assessments obtained during screening will be based on participant’s experience during lifetime and past 1 month. All follow-up visits will be based on participant’s experience since last visit.

The analysis for this scale will be based on the SAF. No safety cut-off will be applied for the SIB data reporting, i.e., all collected data will be used in the analysis.

Patients who answered “yes” to each question in [Table 2-10](#) will be counted by treatment arm and by visit. The descriptive statistics will be provided for the suicidal ideation score (the most severe suicidal ideation) by treatment arm and by visit.

Suicidal ideation and behavior data will be listed. Detailed answers to C-SSRS items will be listed separately for subjects with any suicidal ideation at any time post-baseline (i.e., a ‘yes’ answer to at least one of the five suicidal ideation questions at any time post-baseline) and for a subject with any suicidal behavior at any time post-baseline (i.e., a ‘yes’ answer to at least one of the five suicidal behavior questions at any time post-baseline).

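### Protocol Section 10.2.5 sets a narrower trigger than Section 3 for mandatory overnight admission for suicidality, and ties it to an intravenous infusion that this trial does not give

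*Protocol*

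**What the plan says.** Two current sections of the protocol make an overnight stay for suicidality compulsory.

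- **Section 3 (Study design, extended safety monitoring).** The rule is introduced by "If extended monitoring is required beyond the minimum 4 hours of monitoring on Day 1, the following will be assessed". Under suicidal ideation or behaviour it reads "If moderate to severe suicidal ideation or any suicidal behavior is present, either based on rating scales or investigator judgment, the investigator must hospitalize", for at least one night. There is no condition on how long symptoms have lasted.
- **Section 10.2.5 (Post dose observation / Hospitalization).** After requiring suicidal symptoms of moderate to severe degree, by rating scale or investigator judgement, the sentence continues "such symptoms persist throughout the above mentioned monitoring period following the intravenous infusion, investigators must hospitalize participants at least overnight". The monitoring period it points back to is the four-hour post-dose observation described just before it.

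On route, Section 6.1.4 states: "Participants will receive a single s.c. injection on Day 1". Sections 3 and 6.3.2 agree, and no arm receives an infusion.

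**The concern.** Suicidality is a listed adverse event of special interest, and Section 10.2.5 is where the protocol puts its post-dose hospitalisation guidance. A site that opens that section reads a narrower condition for a compulsory safety action than Section 3 sets, anchored to a procedure that does not occur in this trial. The protocol does not say which section prevails. The cross-references in 10.2.5 name Sections 6.2.3, 9.1.1 and 10.2.4, but not Section 3. With 20 to 25 centres, different sites could apply different admission rules to the same presentation.

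**Working it through.** There is no figure to reproduce. The check is to apply both rules, as worded, to the same cases on Day 1.

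| Case on Day 1 | Section 3 | Section 10.2.5 |
|---|---|---|
| Moderate to severe symptoms present throughout the 4 hours and still present | Overnight stay compulsory | Compulsory, if the infusion is read as the injection |
| Moderate to severe ideation that emerges late, or is first found at the 4-hour C-SSRS | Compulsory | Not compulsory: symptoms did not persist throughout |
| Suicidal behaviour not rated moderate to severe | Compulsory: any behaviour counts | Not compulsory: the severity condition fails |
| Mild ideation | Investigator judgement, with family or friends present for 24 hours | Same |
| Ideation that appears and fully resolves before 4 hours | Not compulsory: the rule governs monitoring beyond 4 hours | Not compulsory |

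The rules therefore differ in the second and third rows and agree in the others.

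**Second row.** The Section 3 release criteria do not allow a participant with new or increased ideation on the C-SSRS to leave at 4 hours. That participant moves to extended monitoring, where Section 3 requires admission if the ideation is moderate to severe. On the wording of 10.2.5 alone, admission is at the investigator's discretion, or recommended if the symptoms are severe.

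**Third row.** Section 10.2.5 speaks of suicidal symptoms. Its own list of events of special interest defines suicidality as ideation or behaviour, so behaviour can be read into the sentence. It must still reach a moderate to severe degree and persist, whereas Section 3 asks for neither.

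**Route.** The infusion reference is wrong on any reading.

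**The case against.** The strongest reply is that both rules can be obeyed at once. Section 10.2.5 gives a sufficient condition for admission. It does not say that admission is compulsory only then, and it permits nothing that Section 3 forbids. A site that follows Section 3 meets both. Section 10.2.5 also has its own safeguards:

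- Events of special interest are followed on site until they resolve or the investigator sees no remaining safety risk.
- Hospitalisation is recommended for severe suicidal symptoms until they resolve.
- Hospitalisation may be prolonged or repeated at any point in the study on the investigator's judgement.

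Persistence can also be read as still being present at the end of observation, which brings 10.2.5 close to Section 3 for ideation. All of this stands and limits the practical gap. It does not remove it: these safeguards are discretionary or recommended where Section 3 sets a fixed rule, the third case above survives the generous reading of persistence, and the route is still wrong.

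A reader might go further and infer that persistence could never be shown with the scheduled scales. Between dosing and the 4-hour point, the C-SSRS and the MADRS are each scheduled once ("The C-SSRS will be assessed at Screening, Baseline (Day 1, -1 hour pre-dose), 4-hour post-dose on Day 1"; "The MADRS score will be measured at Screening, Baseline (Day 1, -1 hour), 4-hour post-dose on Day 1, 24 hours post-dose"), while dissociation and sedation are each rated three times ("The CADSS will be assessed at baseline (Day 1, -1 hour pre-dose), 0.5 hour, 1.5 hour and 4-hour post-dose on Day 1"; "The MOAA/S will be taken at the same visits and time points as CADSS"). The documents do not support that inference. The 4-hour MADRS is rated over the preceding 4 hours (Protocol 8.3.2, SAP 2.5.1.1), and the post-baseline C-SSRS asks about the time since the last visit (Protocol 10.2.4). One interview can therefore cover the whole observation window. The CADSS has a current recall period (Protocol 8.4.4.1), so counting its readings against theirs does not compare like with like. Section 10.2.5 also accepts investigator judgement, and adverse events are collected at 0.33, 0.75, 2 and 4 hours (Table 8-1).

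**Conclusion.** The inconsistency is real and should be corrected. Section 10.2.5 states a narrower compulsory trigger than Section 3 and refers to an infusion that is not part of this trial. The difference is confined to two situations: moderate to severe ideation that emerges late or is first found at the 4-hour C-SSRS, and suicidal behaviour not rated moderate to severe.

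A reader might infer that 10.2.5 lets such participants go home. It does not: nothing in it orders discharge, and the Section 3 release criteria block release at 4 hours for new or increased ideation. What is lost, for a site relying on 10.2.5 alone, is a fixed rule, which is replaced by judgement or recommendation.

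The conclusion rests on reading the persistence clause literally and on reading the monitoring period as the four-hour observation. The first of the two situations narrows if persistence is taken to mean still present at 4 hours; the second does not. The documents give no basis for counting affected participants, and there is no effect on sample size, power, alpha or the primary analysis.

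**What to change.** Replace the trigger sentence in Section 10.2.5 with one that carries Section 3's trigger and time frame. In substance: at or beyond the 4-hour post-dose observation on Day 1, a participant with moderate to severe suicidal ideation, or with suicidal behaviour of any degree, by rating scale or in the investigator's judgement, must be hospitalised at least overnight (see Section 3). Using Section 3's own words behind that time limit would be safest. This removes both the persistence condition and the infusion reference.

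The time limit matters. A sentence covering any symptoms after the injection would also compel admission for ideation that resolves within 4 hours, and for findings at later visits up to Day 29, neither of which Section 3 requires.

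Keep the recommendation on severe symptoms, the discretionary hospitalisation at any point in the study, the mild-symptom rule and the Section 3 release criteria as they are.

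The cost is a wording amendment and a memo to sites. No assessment is added, and no admission becomes compulsory that Section 3 does not already require. Amendment 02 made a similar tidy-up when it removed treatment-interruption wording unsuited to a single-dose study.

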10.3 Committees

10.3.1 Data Monitoring Committee

This study will include a data monitoring committee (DMC) which will function independently of all other individuals associated with the conduct of this clinical trial, including the site investigators participating in the study. The DMC will assess at defined intervals the progress of a clinical trial, review unblinded safety data, and critical efficacy variables and recommend to the sponsor whether to continue, modify, or terminate a trial.

The study may be put on hold and no further enrollment will take place pending full safety data review in case any significant safety finding(s) are observed by the DMC. In case of the study being put on hold, Novartis will promptly notify all concerned investigators/institutions, Ethics Committees/Review Boards and the Regulatory Authorities. The findings and the recommendations of the DMC will be documented and will be made available in the respective Ethics Committees/Review Boards and the Regulatory Authorities.

Specific details regarding composition, responsibilities, data monitoring, and meeting frequency, and documentation of DMC reports, minutes, and recommendations will be described in a separate charter that is established between the sponsor and the DMC.

10.3.2 Steering Committee

The Steering Committee (SC) is established as a group of external experts in the fields of psychiatry with profound knowledge and experience including clinical research in major

depression. These experts may participate in this trial as investigators, but will not be members of the DMC and Novartis representatives from the Clinical Trial Team (CTT).

The SC will ensure transparent management of the study according to the protocol through recommending and approving modifications as circumstances require. The SC will review protocol amendments as appropriate. Together with the CTT, the SC will also develop recommendations for publications of study results including authorship rules. The details of the role of the steering committee will be defined in the steering committee charter.

11 Data Collection and Database management

11.1 Data collection

Data not requiring a separate written record will be defined in the protocol and the Assessment Schedule (Table 8-1) and can be recorded directly on the CRFs. All other data captured for this study will have an external originating source (either written or electronic) with the CRF not being considered as source

All data should be recorded, handled, and stored in a way that allows its accurate reporting, interpretation, and verification.

Designated investigator staff will enter the data required by the protocol into the Electronic Case Report Forms (eCRF). The eCRFs have been built using fully validated secure webenabled software that conforms to 21 CFR Part 11 requirements, Investigator site staff will not be given access to the EDC system until they have been trained. Automatic validation programs check for data discrepancies in the eCRFs, allow modification and/or verification of the entered data by the investigator staff.

The investigator/designee is responsible for assuring that the data (recorded on CRFs) (entered into eCRF) is complete, accurate, and that entry and updates are performed in a timely manner. The Investigator must certify that the data entered are complete and accurate.

After final database lock, the investigator will receive copies of the participant data for archiving at the investigational site.

All data should be recorded, handled, and stored in a way that allows its accurate reporting, interpretation, and verification.

